7.5 HANDLING OF MISSING DATA

Every effort should be made to collect complete data at all visits.

The following rules will be used to impute for missing data:

- For all non-binary endpoints, last observation carried forward (LOCF) will be used to impute missing values
- For all binary endpoints (i.e. endpoints that are either 1 (patient responded) or 0 (patient did not respond)):
 - If no data after that visit*, then impute as failure (NRI [No Response Imputation])
 - If data at visits* before and after, only impute as success if both visits are successes; else impute as failure

* Patients that take prohibited medications to treat Psoriasis will be treated the same as those that discontinued from the trial – i.e. subsequent visits following start of prohibited medication will be considered as failure for binary endpoints.

Missing items from the PRO questionnaires will be handled according to the measure instructions ([Section 10.7](#)). If there is no data for a particular visit, then it will be imputed following the same rules as described above.

Sensitivity analyses to assess the robustness of the hypothesis testing results will include the following methods where applicable:

- LOCF (for binary endpoints)
- Logistic regression

- Mixed effect Model Repeat Measurement (MMRM) (for continuous endpoints)
- Multiple imputation (for binary endpoints)

Of note, for randomized withdrawal analyses, subjects who received retreatment will be counted as non-responders in all visits after the date of retreatment.

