Retreatment: Starting from Week 32, subjects experiencing relapse (defined as an sPGA of ≥ 3), will receive open label risankizumab 150 mg. If this relapse occurs anytime between Week 32 through Week 70, open label risankizumab 150 mg will be administered at 0, 4, and 16 weeks (EOT) after relapse. If this relapse occurs after Week 70 through Week 82, open label risankizumab 150 mg will be administered 0 and 4 weeks (EOT) after relapse. If the relapse occurs after Week 82 through Week 88 the subject will immediately have the EOT procedures performed, including the final dose of study drug.

Follow-Up Period: Subjects who have completed their EOT visit will be followed up for 16 weeks. Follow-up Visit 1 is scheduled at 6 weeks after EOT. And Follow-up Visit 2 is scheduled at 16 weeks after EOT, which is the end of observation (EOO) visit. Subjects who have completed the EOO visit within the specified window, who have not discontinued drug prematurely, and who also meet the eligibility criteria will be offered to roll over into an open label extension study.

Figure 1. Trial Design

BI 655066 is risankizumab.

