10.1.4 Missing Data Imputations

Missing data will be imputed using the following methods for the efficacy analyses:

- Non-Responder Imputation (NRI): the NRI analysis will categorize any subject who does not have evaluation during a specific visit window as a non-responder for that visit. The only exception is when the subject is a responder both before and after a specific visit window, then the subject will be categorized as a responder for the visit. Only observations within the same analysis period will be used except for summary of ITT_A2 from ARM 1, where subjects' observation from Part A1 can be used since the treatment is the

same. The NRI will be the primary approach in the analyses of categorical variables.

- Last Observation Carried Forward (LOCF): The LOCF analyses will use the last observed non-missing evaluation (last completed non-missing evaluation, from composite endpoint) from the previous visit within the particular period for efficacy measures assessed to impute missing data at later visits in the same period. Baseline efficacy evaluations will not be carried forward. Of note, post-baseline observations from Part A1 can be carried forward to ITT_A2 subjects from ARM 1 since treatment is the same. LOCF will be the primary approach in the analyses of continuous variables, and the secondary approach in the analysis of categorical variables.
- As-Observed Cases (OC): The as-observed analysis will not impute values for missing evaluations, and thus a subject who does not have an evaluation on a scheduled visit will be excluded from the as-observed analysis for that visit. As-observed analysis will be the secondary approach in the analysis of continuous variables.
- Multiple Imputation (MI): The MI will be used as sensitivity approach to impute missing data in primary and ranked secondary endpoints. The variables to be included in the imputation model are listed below. If MI is not applicable due to the nature of our data (e.g., MCMC algorithm does not converge), logistic regression or mixed effect model repeat measurement (MMRM) methods will be applied as sensitivity approach, whichever applicable.

The Multiple Imputation analysis will be carried out in three steps.

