- Imputation of missing data. The imputation will be generated for each efficacy endpoint measurement. The variables to be included in the imputation model are: Baseline disease severity (PASI and sPGA), Baseline weight (continuous variable), treatment group, actual prior TNF antagonist exposure, and measurements at each visit from randomization (or re-randomization) up to the end of the analysis period. For each endpoint, 20 'complete' datasets will be generated using SAS PROC MI. The imputed post-baseline measurements

will be rounded to the same precision as the observed data before the determination of responder status (e.g., PASI 90).

- Analysis of imputed data sets. A CMH test, stratified by stratification factors, will be used to analyze categorical endpoints in each imputed dataset.
- Synthesis of imputation and analysis results. SAS PROC MIANALYZE will be used to generate the final inferences of the risk difference between treatment groups.

Of note, subjects who discontinued due to AE of "Worsening of disease under study," or received retreatment with risankizumab for relapse during Part B, will be counted as non-responders in all visits thereafter in the NRI and MI analyses, and will have their last observation prior to discontinuation or retreatment with risankizumab carried forward in the LOCF analyses.

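### SAP 10.1.4 leaves the protocol's retreatment-is-non-response rule out of the LOCF analyses, so some relapsed patients would remain PASI 50/75/90 responders

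*SAP*

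**What the plan says.** Protocol 7.5 lists the sensitivity methods, including LOCF for binary endpoints. It closes with a rule for the randomised withdrawal analyses: "subjects who received retreatment will be counted as non-responders in all visits after the date of retreatment". No method is exempted.

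SAP 10.1.4 splits this rule by method. Patients retreated for relapse in Part B "will be counted as non-responders in all visits thereafter in the NRI and MI analyses", but "will have their last observation prior to discontinuation or retreatment with risankizumab carried forward in the LOCF analyses". On the standing of each method, the same section says: "The NRI will be the primary approach in the analyses of categorical variables"; and "LOCF will be the primary approach in the analyses of continuous variables, and the secondary approach in the analysis of categorical variables". MI is confined to the primary and ranked secondary endpoints.

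Retreatment is triggered by sPGA alone: "subjects experiencing relapse (defined as an sPGA of ≥ 3), will receive open label risankizumab 150 mg" (SAP 4.2).

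SAP 14.1, which lists the changes from protocol to SAP, does not mention a different rule for LOCF.

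**The concern.** The protocol treats retreatment as an outcome, not as missing data. The reason recorded in its amendment log (global amendment 2.0, Section 7.5) is that retreatment is given for lack of efficacy, and that reason does not depend on how missed visits are imputed. SAP 10.1.3 agrees: retreatment is a failure in the time-to-loss analyses. One patient could therefore be a failure under NRI, MI and time to loss, yet a PASI responder under LOCF.

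Two sets of results are at stake.

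- **PASI 75 and PASI 90 at Week 52 in ITT_B_R.** MI does not extend to these endpoints, so LOCF is the only alternative to NRI that the SAP names for them. A gap between the two would mix the handling of missed visits with relapsers rescored as responders.
- **PASI categories after Week 52, at the Week 52 analysis.** SAP 10.1 stops all other analyses at Week 52 but continues the categorical PASI and sPGA endpoints under LOCF to the last visit with any observed data. No other method is applied there, and retreatment will have accumulated.

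**Working it through.** **1. Which value is carried.** Protocol 6.2.2 puts all visit procedures before dosing. SAP Table 8, footnote b, ends the Part B window at the first retreatment dose date. The carried value is therefore the pre-dose relapse-visit value.

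**2. Endpoints that cannot be affected.** At that visit sPGA is at least 3, which is already non-response for sPGA 0/1 and sPGA 0. Signs are present, so PASI is above 0 and PASI 100 is not met.

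**3. Endpoints that can be affected.** The sPGA scoring key (Protocol Appendix 10.2) gives a 3 when the mean of the three signs is at least 2.5. With integer scores, the sign sum is at least 8. PASI (Appendix 10.1) multiplies each region's sign sum by an area score and by a weight of 0.1 head, 0.3 trunk, 0.2 upper or 0.4 lower extremities. Take sign sum 8 and area score 1, with example baselines of 12 (the entry minimum) and 20:

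| Regions involved | PASI | Reduction from 12 | Reduction from 20 |
|---|---|---|---|
| Upper extremities | 0.2 × 8 = 1.6 | 86.7% | 92% |
| Lower extremities | 0.4 × 8 = 3.2 | 73.3% | 84% |
| Upper and lower | 0.6 × 8 = 4.8 | 60% | 76% |
| All four | 1.0 × 8 = 8.0 | 33.3% | 60% |

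Some relapsed patients still meet PASI 50, 75 or 90 and others do not.

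**4. The plan's own figure.** Protocol 7.7 assumes sPGA 0/1 response of 90% versus 75% at Week 52, 1:2 allocation, two-sided 0.05 and 90% power. With pooled variance the mean proportion is (0.90 + 2 × 0.75)/3 = 0.80, and

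n = [1.960 × √(1.5 × 0.80 × 0.20) + 1.282 × √(0.90 × 0.10 + 0.75 × 0.25/2)]² / 0.15² = 101.3, rounded up to 102.

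This gives 102:204, with power 90.2%; 306/0.8 = 382.5, rounded up to 383. The stated figures reproduce.

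**5. Effect on the LOCF difference.** Let rA and rB be the shares relapsed and retreated before the visit on continued drug and on withdrawal. Let fA and fB be the shares of those whose relapse-visit PASI still meets the threshold. Then

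LOCF difference = difference under the protocol rule + fA × rA − fB × rB.

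With fA = fB = f, the difference shrinks by f × (rB − rA).

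The documents give no relapse rates, no f and no PASI planning rates. The illustration borrows the 15-point sPGA difference. It takes as relapses either all of the planned 10% and 25% losses of sPGA 0/1, or half of them:

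| f | rA 10%, rB 25% | rA 5%, rB 12.5% |
|---|---|---|
| 0 (protocol rule) | 15 | 15 |
| 0.1 | 15 − 1.5 = 13.5 | 15 − 0.75 = 14.25 |
| 0.3 | 15 − 4.5 = 10.5 | 15 − 2.25 = 12.75 |
| 0.5 | 15 − 7.5 = 7.5 | 15 − 3.75 = 11.25 |

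For scale, the standard error at 102:204 with these rates is √(0.09/102 + 0.1875/204) = 4.2 points.

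**6. Direction.** With rA 10% and rB 25%, the difference widens once fA/fB exceeds 25/10 = 2.5. For example, fA = 0.5 and fB = 0.1 give 15 + 5 − 2.5 = 17.5 points.

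**7. Relapse at the visit being analysed.** The protocol rule starts after the retreatment date, so a relapse-visit PASI at Week 52 itself is scored the same under both documents. Only earlier retreatment counts towards rA and rB.

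**The case against.** The SAP clause is explicit and prespecified, and part of it is needed: LOCF is primary for continuous endpoints, where non-response has no meaning. NRI, the primary method for binary endpoints, follows the protocol. PASI 75/90 at Week 52 are other secondary endpoints outside the testing hierarchy. Where the rule shrinks the difference it works against continued treatment, so it could not then create a favourable result. All of this stands, and it limits the point to the binary LOCF analyses.

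The PASI examples are also favourable to the concern. They use the lowest area score and assume that sPGA signs, averaged over all lesions, carry over to the regional PASI signs. Appendix 10.2 also remarks that a lower sPGA means less body coverage, although its scoring key contains no area term. The examples show that the misclassification is possible, not how common it is.

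A reader might infer more than the documents support:

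- **That relapsed patients in general become PASI responders.** Only those whose relapse-visit PASI still meets the threshold do.
- **That the Part B primary result is biased.** sPGA 0/1 at Week 52, and the ranked secondary at Week 104, carry forward a failing value. The exception would be a program that took the last value strictly before the retreatment date; Table 8, footnote b, points away from that reading.
- **That a gap between NRI and LOCF would show only this rule.** The two also differ for patients who miss visits for other reasons.
- **That a bias of known size toward zero is established.** The documents give neither f nor the relapse rates.

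**Conclusion.** The inconsistency is real and undeclared. Protocol 7.5 covers LOCF; SAP 10.1.4 exempts it, contrary to its own time-to-loss definition. In the LOCF analyses, some relapsed and retreated patients would count as PASI 50/75/90 responders at later Part B visits.

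The likely effect is a smaller withdrawal difference: 0.75 to 7.5 points over the illustrated values. That range rests on f of 0.1 to 0.5, equal f in both arms, relapse rates set at all or half of the planned sPGA losses, and a PASI difference borrowed from the sPGA plan. It is not an estimate, and markedly unequal f could reverse the sign.

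sPGA 0/1, sPGA 0 and PASI 100 are not affected, and no confirmatory conclusion changes. The point matters for LOCF as "the secondary approach in the analysis of categorical variables" when applied to PASI 75/90 at Week 52, and most for PASI categories beyond Week 52 at the Week 52 analysis.

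**What to change.** In SAP 10.1.4, state that for binary endpoints in the ITT_B_R comparison of continued drug with withdrawal, the LOCF analyses also set non-response at every Part B visit after the date of first retreatment. Use LOCF only for visits missing for other reasons. Keep the carry-forward rule for continuous endpoints, and leave unchanged the separate continuous-treatment summary (SAP 5.1 and the note to Table 8), which includes post-retreatment data by design.

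If the sponsor prefers the current rule, list it in SAP 14.1 with a reason and define the carried value as the pre-dose relapse-visit assessment.

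The cost is one sentence and a small programming change, with no new data. LOCF response rates for PASI 50/75/90 can only stay the same or fall.

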10.2 Primary Efficacy Analysis

10.2.1 Primary Efficacy Analysis in Part A

There are two co-primary endpoints to assess the efficacy of risankizumab 150 mg for the treatment of moderate to severe plaque psoriasis in Part A. These are as follows:

- Achievement of $\geq 90\%$ reduction from baseline PASI score (PASI 90) at Week 16
- Achievement of an sPGA of clear or almost clear (0 or 1) at Week 16

The primary null hypotheses are that risankizumab 150 mg is not different from placebo in achieving PASI 90 and in achieving sPGA of clear or almost clear at Week 16.

The achievement of PASI 90 at Week 16 is the first co-primary endpoint. The difference in proportion of subjects achieving PASI 90 between treatment arms will be estimated and tested using the Cochran-Mantel-Haenszel risk difference estimate stratified by the stratification factors of baseline weight (≤ 100 kg vs. > 100 kg) and prior exposure to TNF antagonists (0 vs. ≥ 1).

The achievement of a sPGA of clear or almost clear at Week 16 is the second co-primary endpoint. The analysis method for the sPGA co-primary endpoint will be identical to that of the PASI 90 co-primary endpoint detailed above.

The co-primary endpoints of PASI 90 and sPGA clear or almost clear need to be significant simultaneously. Both endpoints will be tested using a two-sided test with a type I error rate of 0.05.

The primary analysis will be carried out in the ITT_A1 Population and the PP_A1 Population. Non-responder imputation will be used as the primary approach for missing values. LOCF and MI will be performed as sensitivity analyses.

10.2.2 Primary Efficacy Analysis in Part B

Achievement of an sPGA of clear or almost clear (0 or 1) at Week 52 is the primary endpoint for Part B under re-randomization. This endpoint will be tested independently with a type I error rate of 0.05, for the ITT_B_R Population. A sensitivity analysis will also be performed on the same endpoint for the PP_B_R Population.

10.3 Secondary Efficacy Analyses

10.3.1 Ranked Secondary Efficacy Analysis

10.3.1.1 Ranked Secondary Efficacy Analysis in Part A

The ranked secondary endpoints in Part A are in ranked order as follows:

1. Achievement of $\geq 75\%$ reduction from baseline PASI score (PASI 75) at Week 16
2. Achievement of 100% reduction from baseline PASI score (PASI 100) at Week 16
3. Achievement of sPGA of clear at Week 16
4. Achievement of DLQI score of 0 or 1 at Week 16

Ranked secondary endpoints above will be analyzed for the ITT_A1 Population. The same methods as discussed for the primary analyses will be used. The following null hypotheses will be tested in a hierarchical order using two-sided tests with a type I error of 0.05 only if the null hypothesis for the co-primary endpoints in Part A1 has been rejected:

1. Risankizumab is not different from placebo with respect to PASI 75 response at Week 16
2. Risankizumab is not different from placebo with respect to PASI 100 response at Week 16
3. Risankizumab is not different from placebo with respect to achieving an sPGA of clear at Week 16
4. Risankizumab is not different from placebo with respect to achieving a DLQI score of 0 or 1 at Week 16.

10.3.1.2 Ranked Secondary Efficacy Analysis in Part B

The ranked secondary endpoint for Part B is the achievement of sPGA of clear or almost clear (0 or 1) at Week 104.

This ranked secondary endpoint will be analyzed for the ITT_B_R Population. The same methods as discussed for the primary analyses will be used.

The null hypotheses below will be tested in a hierarchical order in the final analysis only, using two-sided tests with a type I error of 0.05 only if the null hypothesis for the primary endpoint in Part B has been rejected:

- Continuation of risankizumab is not different from switching to placebo with respect to sPGA of clear or almost clear (0 or 1) response at Week 104.

10.3.2 Other Secondary Efficacy Analysis

The other secondary endpoints are as follows:

- Achievement of PASI 75 at Week 52
- Achievement of PASI 90 at Week 52
- Achievement of PASI 100 at Week 52

Other secondary endpoints will be analyzed among the ITT_B_R Population.

10.3.3 Further Efficacy Endpoints

The further endpoints are as follows:

- Achievement of PASI 50 at all visits collected
- Achievement of PASI 75 at all visits collected
- Achievement of PASI 90 at all visits collected
- Achievement of PASI 100 at all visits collected
- Time to the first achievement of PASI 50, PASI 75, PASI 90, and PASI 100
- Time to loss of PASI 50, PASI 75, PASI 90, and PASI 100 response for subjects re-randomized at Week 28
- Change and percent change from baseline in PASI at all visits collected
- Achievement of PASI < 3 at all visits collected
- Proportion of subjects with at least 25% increase in PASI from baseline within 60 days after re-randomization for subjects re-randomized to placebo at Week 28
- Achievement of sPGA of clear or almost clear at all visits collected
- Achievement of sPGA of clear at all visits collected
- Time to the first achievement of sPGA of clear or almost clear
- Time to loss of sPGA of clear or almost clear response for subjects re-randomised at Week 28
- Time to sPGA of ≥ 3 (relapse) for subjects re-randomised at Week 28
- Change from baseline in DLQI at all visits collected

- Achievement of a DLQI score of 0 or 1 at all visits collected
- Achievement of a reduction of 5 or more points from baseline in DLQI score at all visits collected, among subjects with baseline $DLQI \geq 5$
- Change from baseline in HAQ-DI at all visits collected, among subjects with PsA confirmed via ClASsification of Psoriatic Arthritis (CASPAR) and had baseline value > 0
- Achievement of a reduction of 0.3 or more from baseline HAQ-DI at all visits collected, among subjects with PsA confirmed via CASPAR and had baseline value ≥ 0.3
- Change and percent change from baseline on patient Pain VAS, among subjects with PsA confirmed via CASPAR and had baseline value > 0
- Achievement of a reduction of 10 or more from baseline Pain VAS at all visits collected, among subjects with PsA confirmed via CASPAR and had baseline value ≥ 10
- Change and percent change from baseline on patient Global Assessment VAS, among subjects with PsA confirmed via CASPAR and had baseline value > 0
- Change from baseline in Swollen or Tender Joint Count (28 joints) at all visits collected, among subjects with PsA confirmed via CASPAR and had baseline value > 0
- Change from baseline in DAS28 at all visits collected, among subjects with PsA confirmed via CASPAR and had baseline value > 0
- Change and percent change from baseline in Nail Psoriasis Severity Index (NAPSI) at all visits collected, in subjects with baseline NAPSI > 0
- Change and percent change from baseline in Palmoplantar Psoriasis Severity Index (PPASI) at all visits collected, in subjects with baseline PPASI > 0
- Change and percent change from baseline in Psoriasis Scalp Severity Index (PSSI) at all visits collected, in subjects with baseline PSSI > 0

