5.1.3 Further Endpoints

The further endpoints are as follows:

- Achievement of PASI 50 at all visits collected
- Achievement of PASI 75 at all visits collected
- Achievement of PASI 90 at all visits collected
- Achievement of PASI 100 at all visits collected
- Time until the first achievement of PASI 50, PASI 75, PASI 90, and PASI 100

- Time until loss of PASI 50, PASI 75, PASI 90, and PASI 100 response for patients re-randomised at Week 28
- Change and percent change from baseline in PASI at all visits collected
- Absolute PASI of < 3 at all visits collected
- Achievement of an sPGA score of clear or almost clear at all visits collected
- Achievement of an sPGA score of clear at all visits collected
- Time until the first achievement of sPGA of 0 or 1
- Time until loss of sPGA of 0 or 1 response for patients re-randomised at Week 28
- Time until sPGA score of ≥ 3 (relapse) for patients re-randomised at Week 28
- Change from baseline in DLQI at all visits collected
- Achievement of a DLQI score of 0 or 1 at all visits collected
- Achievement of a reduction of 5 or more points from baseline in DLQI score at all visits collected
- Change from baseline in HAQ-DI at all visits collected, in patients selected for PsA assessment.
- Change and percent change from baseline on patient Pain VAS
- Change and percent change from baseline on patient Global Assessment VAS
- Change from baseline in Swollen or Tender Joint Count (28 joints) at all visits collected in patients selected for PsA assessment.
- Change from baseline in DAS28 at all visits collected in patients selected for PsA assessment.
- Change and percent change from baseline in Nail Psoriasis Severity Index (NAPSI) at all visits collected
- Change and percent change from baseline in Palmoplantar Psoriasis Severity Index (PPASI) at all visits collected
- Change and percent change from baseline in Psoriasis Scalp Severity Index (PSSI) at all visits collected
- Change of metabolic risk factors from baseline (waist circumference, body weight, HOMA-index)

See the Flow Chart for when the above measures are collected. The above endpoints will be analyzed, where appropriate, for re-randomized subjects after receiving open-label study drug for retreatment (Flow Chart 2 and 3).

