10.6 DIAGNOSIS AND ASSESSMENTS FOR PATIENTS WITH PSORIATIC ARTHRITIS (AT SELECTED SITES ONLY)

At Visit 1 at selected study sites, patients with a positive history of PsA or suspected to have PsA will be further evaluated for PsA diagnosis based on CASPAR (ClASsification of Psoriatic Arthritis) criteria ([R15-1001](#)).

To be classified as having PsA, a patient must have inflammatory articular disease (joint, spine, or enthesal) with at least 3 points total from the 5 categories in Table 10.6: 1. All trial participants will have 2 points assigned due to evidence of current psoriasis per trial entry criteria and will require at least one additional point for diagnosis of PsA.

Table 10.6:1 CASPAR criteria

Category	Point assignment
Evidence of current psoriasis, a personal history of psoriasis, or a family history of psoriasis	2 points
Typical psoriatic nail dystrophy, including onycholysis, pitting, or hyperkeratosis observed on current physical examination	1 point
A negative test result for rheumatoid factor by any method except latex	1 point
Either current dactylitis, defined as swelling of an entire digit, or a history of dactylitis recorded by a rheumatologist	1 point
Radiographic evidence of juxta-articular new bone formation appearing as ill-defined ossification near joint margins (but excluding osteophyte formation) on plain radiographs of the hand or foot	1 point

If a diagnosis of PsA is confirmed by CASPAR and the patient meets all study entry criteria for participation, the following will be performed at Visit 2.

- HAQ-DI (see [Appendix 10.7.2](#))
- Pain VAS (see [Appendix 10.7.3](#))
- Patient global assessment VAS (see [Appendix 10.7.4](#))
- Tender or Swollen joint counts (TJC/SJC) on 28 joints (refer to [Table 10.6: 2](#))
- Entry of data for calculation of DAS28 on electronic device (Refer to [Appendix 10.6.1](#))

During the treatment period and EOO the following will continue to be performed at the visits noted in the Flow Charts if the TJC/SJC is ≥ 3 at Visit 2.

- HAQ-DI (see Appendix 10.7.2)
- Pain VAS (see Appendix 10.7.3)
- Patient global assessment VAS (see Appendix 10.7.4)
- Tender or Swollen joint counts (TJC/SJC) on 28 joints (refer to Table 10.6: 2)
- Entry of data for calculation of DAS28 on electronic device (Refer to Appendix 10.6.1)

Proprietary confidential information © 2016 Boehringer Ingelheim International GmbH or one or more of its affiliated companies
Table 10.6:2 Tender or Swollen Joint Count (28)

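### Two psoriatic arthritis responder endpoints keep patients whom Appendix 10.6 does not schedule for reassessment, and NRI then counts those patients as failures

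*SAP*

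**What the plan says.** Three rules bear on this point.

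- **Denominator (SAP 10.3.3).** The HAQ-DI responder endpoint is "Achievement of a reduction of 0.3 or more from baseline HAQ-DI at all visits collected, among subjects with PsA confirmed via CASPAR"; the same line goes on to require a baseline value of at least 0.3. The Pain VAS endpoint is "Achievement of a reduction of 10 or more from baseline Pain VAS at all visits collected, among subjects with PsA confirmed via CASPAR", with a baseline value of at least 10. Neither mentions a joint count.
- **Who is assessed, and when (Protocol Appendix 10.6).** The rule for Visit 2 begins "If a diagnosis of PsA is confirmed by CASPAR and the patient meets all study entry criteria for participation, the following will be performed at", and HAQ-DI and Pain VAS are on its list. After that, "the following will continue to be performed at the visits noted in the Flow Charts if the TJC/SJC is ≥ 3 at Visit 2".
- **Missing data (SAP 10.1.4).** Under NRI, "the NRI analysis will categorize any subject who does not have evaluation during a specific visit window as a non-responder for that visit". One carve-out is allowed, for someone who responds at visits on both sides of the gap. NRI is primary for categorical variables. LOCF is secondary for them and does not carry baseline forward.

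The protocol's own HAQ-DI endpoint in Section 5.1.3 is continuous: "Change from baseline in HAQ-DI at all visits collected, in patients selected for PsA assessment". The responder versions do not appear in that section, and SAP 14.1 does not list them among its changes from the protocol.

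**The concern.** NRI is meant for patients who should have been evaluated and were not. Here it also catches patients for whom the protocol schedules no later evaluation. Such a patient has a qualifying baseline score, enters the denominator, and cannot be recorded as a responder whatever happens to the joints.

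The reported response rates would then depend partly on how many patients had few affected joints at Visit 2. Improvement in psoriatic arthritis is a stated trial objective (Protocol 2.2), and these two endpoints give it in responder form, so the figures should describe patients whose response was measured.

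**Working it through.** **Step 1. Follow one patient through the rules.** Take a patient at a selected site, CASPAR-confirmed, with Pain VAS of 10 or more and a Visit 2 joint count below 3.

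| Rule | Result for this patient |
|---|---|
| Appendix 10.6, Visit 2 | HAQ-DI and Pain VAS collected, so a baseline exists |
| Appendix 10.6, treatment period and EOO | Not scheduled again |
| SAP 10.3.3 | In the Pain VAS denominator (and in the HAQ-DI one if baseline is at least 0.3) |
| SAP 10.1.4, NRI | Non-responder at each visit |
| SAP 10.1.4, NRI exception | Needs response both before and after the window; impossible with no post-baseline value |
| SAP 10.1.4, LOCF | No value, because baseline is not carried forward |

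Protocol 7.5 gives the same NRI result: with no later data, the visit is a failure.

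**Step 2. Can such patients exist?** Yes, on the documents' own definitions. Appendix 10.6 accepts joint, spinal or entheseal disease as the entry condition for CASPAR. Every participant starts with 2 of the 3 points needed, so a negative rheumatoid factor can supply the third. The 28-joint table covers shoulder, elbow, wrist, hand and knee, but not hip, ankle or foot. Disease outside those joints can give pain or disability with a low count. The baseline cuts are on other measures and do not remove these patients.

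**Step 3. Size.** The documents state no figure to reproduce: not the size of the PsA subset, the share below the threshold, or any HAQ-DI or Pain VAS response rate. Let f be the share of the denominator below the threshold and p the response rate among patients who are followed. For each arm:

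observed rate = f × 0 + (1 - f) × p = (1 - f)p

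With the same f in both arms, the observed difference is (1 - f)(p₁ - p₀). For illustration only, assume p₁ = 50% and p₀ = 25%:

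| f (assumed) | Active | Placebo | Difference |
|---|---|---|---|
| 0 | 50% | 25% | 25 points |
| 10% | 45% | 22.5% | 22.5 points |
| 30% | 35% | 17.5% | 17.5 points |
| 50% | 25% | 12.5% | 12.5 points |

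**Step 4. Unequal f.** Neither randomisation is stratified by PsA (Protocol 7.6), so f can differ by chance in a small subset. The difference is then p₁(1 - f₁) - p₀(1 - f₀). With f of 40% active and 20% placebo it is 0.50 × 0.60 - 0.25 × 0.80 = 10 points. With the shares reversed it is 0.50 × 0.80 - 0.25 × 0.60 = 25 points.

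**Step 5. Precision.** Restricting the denominator loses patients but removes the dilution. Assume an 80:20 subset, f = 30%, and a two-sided 5% test of two proportions with pooled null variance. Power is 30% as planned (35% v 17.5%, 80:20) and 38% after restriction (50% v 25%, 56:14). At f = 50% the figures are 18% and 28%. The SAP test uses separate arm variances. Without strata, at f = 30%:

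- As planned: 0.175 / √(0.35 × 0.65/80 + 0.175 × 0.825/20) = 1.74, so power is Φ(1.74 - 1.96), about 41%.
- Restricted: 0.25 / √(0.25/56 + 0.1875/14) = 1.87, so power is Φ(1.87 - 1.96), about 46%.

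The levels depend on the assumptions. In these cases restriction does not cost power.

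**The case against.** **The joint-count condition stands in one place only.** The Flow Chart footnotes and Protocol 6.2 assign these assessments to PsA patients at selected sites without repeating it. If sites follow the Flow Charts alone, patients below 3 are assessed, NRI does not touch them, and a restricted denominator would discard real data. This stands as an inconsistency to reconcile. It does not remove the point, because Flow Chart footnotes 3 and 16 and the PsA paragraph of Section 6.2.2 send the reader to Appendix 10.6, which sets the condition.

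**The baseline cuts may already exclude many of these patients.** They may, since low pain or disability plausibly goes with few affected joints. A reader might infer that all CASPAR-confirmed patients are counted. They are not, and f may be small.

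**Other planned analyses avoid the problem.** LOCF for the responder endpoints, and LOCF and as-observed analyses for the continuous endpoints, leave these patients out. That is true, but LOCF is secondary for categorical variables, so the primary result keeps the dilution and the denominators differ between analyses.

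**Restriction changes the question.** It does, because response in unfollowed patients is unknown. The restricted analysis describes patients with at least the threshold joint count and does not recover a value for everyone with PsA.

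**Conclusion.** The point holds on the text. Followed exactly, the plan scores as non-responders, at every post-baseline visit, patients above the baseline cut whom Appendix 10.6 does not schedule for reassessment. Relative to the patients followed, each rate is multiplied by (1 - f), and the difference likewise if f is equal across arms. The size is unknown because f is not in the documents; the tabulated values are illustrations.

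Two stronger readings are not supported. A reader might infer bias in favour of the drug. The Visit 2 count precedes treatment, so f is expected to be similar in both arms and the expected effect is shrinkage of the difference towards zero; chance imbalance could move it either way. A reader might also infer that the trial's main conclusions, or the PsA objective as a whole, are at risk. Only two further endpoints, added in the SAP and outside the testing hierarchy, are affected. The protocol's continuous PsA endpoints do not use NRI, and primary and ranked results do not change.

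The conclusion assumes that sites and the electronic device apply the Appendix 10.6 condition.

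**What to change.** 1. In SAP 10.3.3, limit the HAQ-DI (reduction of at least 0.3) and Pain VAS (reduction of at least 10) responder endpoints to CASPAR-confirmed patients above the baseline cut who met the Visit 2 joint-count condition for continued PsA assessment. Alternatively, state in SAP 10.1.4 that NRI does not apply to assessments not scheduled by design.
2. Define whether a TJC/SJC of at least 3 means tender, swollen, either or the sum, matching what the electronic device implements. Without this the filter cannot be programmed.
3. Reconcile the Flow Chart footnotes with Appendix 10.6, and check before database lock whether patients below the threshold were in fact reassessed. If they were, choose between the two options in item 1 with that in mind.
4. Report the number above the baseline cut but below the threshold in each arm, so that f is visible.

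The cost is a few lines of SAP text, one clarification of the protocol wording, and a filter on a variable already collected at Visit 2. The filter does not condition on post-randomisation data.
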